3.4.2. Other Clinical Outcome Assessments (COAs)

The Amsterdam Instrumental Activities of Daily Living Questionnaire was chosen following a review of currently available measures and examination of their previous performance in both epidemiological studies and clinical trials. Selection criteria were the following:

- Known neurophysiological links to cognition
- Sensitive to at least Mild Cognitive Impairment
- Good repeat-test reliability
- Validated in European countries
- Dimensional or otherwise able to demonstrate change over time

Changes in everyday activities in pre-clinical AD are detectable only using scales specifically designed for this purpose – the more widely used Activities of Daily Living (ADL) and Instrumental Activities of Daily Living (IADL) questionnaires are unlikely to be sensitive to very early changes.

Everyday Functioning

The Amsterdam Instrumental Activities of Daily Living Questionnaire^{27,28}

This is an informant-report checklist recorded by the clinician, aimed at detecting early activities of daily living changes associated with pre-clinical stage dementia. The test has high internal consistency and retest reliability with construct validity established by comparing estimated trait levels with clinical and demographic measures.

This assessment will be done annually.

3.4.3. CSF Biomarker Outcomes

All participants will have a lumbar puncture performed at baseline (Visit 1) and at 2 years (Visit 4) and every second year thereafter. We believe that a CSF collection every two years will be sufficient to reflect any changes in the biomarkers associated with AD related biomarkers.

If an attempt(s) at collecting the sample (CSF) is made at Visit 1, and no sample is obtained, then approval should be sought from the Medical Monitor on the participant's continuation in the trial. Attempts should be made at Visit 2 or Visit 3 to collect a sample from the participant. If no sample is obtained in these future visits, then there should be further discussion with the Medical Monitor. Participants may remain in the study despite being unable to provide a CSF sample as they are still contributing valuable biological samples, images and cognitive data all of which will advance the understanding of Alzheimer's Disease.

Participants may become unable for medical reasons to undergo a lumbar puncture after the baseline visit. These participants will be allowed to remain in the study without completing lumbar punctures at future time-points. Participants who score >1 on the CDR will remain in the cohort and will not complete further lumbar punctures or MRI sampling at Visit 4 or any other future visits.

A common protocol for sample collection, storage and shipment will be used at all EPAD TDCs. Measurements will include AD-related markers ($A\beta$, t-tau and p-tau), neurofilament light, TREM 2, and neurogranin and this data will be used for disease modelling and for staging of disease pathology. All details of CSF sampling will be provided in the accompanying laboratory manual.

If an individual participant has had a lumbar puncture and CSF sample collected and stored according to the CSF sampling manual procedure (included in the laboratory manual) within 12 months prior to Visit 1, then this sample can be provided for analysis for the Visit 1 baseline data. Those participants who qualify for EPAD LCS and who have had a previous lumbar puncture performed within 12 months prior to the baseline visit, are still required to have a baseline MRI scan unless they have had an MRI performed to the specifications in the Core EPAD scanning protocol in the 12 months prior to Visit 1 as per section 3.4.4. of the protocol. If a participant has had a PET amyloid scan in the last 12 months, with results available to EPAD TDC for review and the participant is aware of PET results, they may choose to defer the baseline lumbar puncture to the 12 month visit. All participants are expected to have at least one lumbar puncture performed as part of the EPAD LCS.

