1. INTRODUCTION

1.1. Background

Alzheimer's disease (AD) is the leading cause of dementia globally affecting ~7 million people in Europe¹. As the population ages, the number of people with dementia will rise and a concomitant rise in the dependency ratio² means that the economic burden of AD will increase dramatically from an already high baseline (~€262 billion in 2015)³. Attempts to impact on disease progression pharmacologically in symptomatic populations remain ongoing, but recent results have been disappointing⁴. There is now consensus that the genesis of AD pathology predates dementia onset by over 20 years^{5,6}, presenting an opportunity for disease course modification before dementia onset and even prior to the appearance of clinical symptoms. With numerous biologically active agents in late phase trials which affect a range of pathological processes in AD (e.g. anti-oligomerisation, secretase inhibitors, kinase inhibitors and anti-amyloid monoclonal antibodies), the key challenge is to accurately identify individuals with high probability of subsequent AD dementia development, who are suitable for trial inclusion and willing to participate in secondary prevention studies. Current proposals for defining an individual's probability for developing AD dementia based on either biomarkers or clinical symptoms have been focused on the stage of AD close to dementia onset. Disease models and their phenotypic expression needed for probability estimation in earlier stages in the disease process are less well defined but the subject of intense study currently. It is important to firstly develop accurate disease models for AD in early disease stages when people do not yet have symptoms, or express only subjective complaints of cognitive decline, or have only mild cognitive symptoms. These people need to be followed-up longitudinally, and they could be recruited into trials designed to reduce early disease burden or decrease the probability of developing AD dementia.

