3.2. Study Description and Rationale for Design Elements

3.2.1. Flow of Research Participants from PCs to EPAD LCS

Research participants will mainly be recruited from existing PCs across Europe. This provides the major advantage of shortened recruitment process into EPAD LCS. Selection of PCs for EPAD does not imply sharing of PCs data with EPAD, and EPAD will not have access to individual-level data from PCs.

There will be two classes of PCs considered for EPAD LCS (Table 1). The classes differ in way of research participant recruitment, and type of data, and hence suitability for EPAD.

Table 1: Classes of PCs

Research cohorts	Observational study with research participants from the general population
	Observational study with research participants recruited from other sources
	Prevention trial
	Pre-existing trial readiness cohort
Clinical/routine care cohorts	Memory clinic based
	General practitioner/primary care based

To ensure the engagement of PCs, they will be selected based on close connections with core partners in the EPAD Consortium, maximally leveraging those involved in European Medical Information Framework (EMIF, <http://www.emif.eu/>) and regional initiatives like the Dementias Platform UK (DPUK, <http://www.dementiasplatform.uk/>). EMIF is highly relevant in the context of EPAD because it aims to develop a common information framework of participant-level data that will link up and facilitate access to diverse medical and research data sources, opening up new avenues of research. Importantly, AD is included in EMIF as one of the initial research areas to provide a focus and guidance for the development of the framework. The EMIF Platform will initially be able to, on its own, leverage data on around 40 million European research participants by means of federation of healthcare databases and cohorts from 7 different countries, designed to be representative of the different types of existing data sources (population-based registries, hospital-based databases, cohorts, national registries, biobanks, etc.). The DPUK is developed and led by the UK Medical Research Council, and aims to accelerate progress in early detection, improved treatment and ultimately prevention of dementias. The DPUK is creating the world's largest population study for use in dementia research, bringing together two million participants aged 50 and over, from over 30 existing cohort studies and registers within the UK.

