8. Any contraindications for Lumbar Puncture at visit 1 (including refusal of lumbar puncture procedure to collect sample)
9. Any evidence of intracranial pathology which, in the opinion of the Investigator, may affect cognition including but not limited to brain tumours (benign or malignant), aneurysm or arteriovenous malformations, territorial stroke (excluding smaller watershed strokes), recent haemorrhage (parenchymal or subdural), or obstructive hydrocephalus. Research participants with a MRI scan demonstrating markers of small vessel disease (e.g. white matter changes or lacunar infarcts) judged to be clinically insignificant, or microbleeds are allowed.
10. Participation in a clinical trial of an investigational product (CTIMP) in the last 30 days⁷. Participation in a non-CTIMP or an observational arm of a CTIMP is not considered an exclusion criterion. Co-enrolment in the Amyloid Imaging to Prevent Alzheimer's Disease (AMYPAD) Prognostic and Natural History Study (PNHS) is not considered to fall under this exclusion criteria.
11. Diminished decision-making capacity/not capable of consenting at Visit 1.
12. Unable to comply with protocol requirements in the opinion of the investigator

If at a subsequent annual EPAD LCS visit health professionals suspect diminished consent capacity according to local TDC routine procedures, a formal assessment of the research participant's capacity to consent will be conducted (e.g. University of California, San Diego Brief Assessment of Capacity to Consent, UBACC⁷). The participant will be offered the opportunity to continue in the EPAD LCS under suitable local regulations regarding capacitous participants who have consented to enter a longitudinal study who subsequently lose capacity.

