If an individual participant has had an MRI to the specification in the Core EPAD Scanning protocol in the 12 months prior to Visit 1, then this scan can be provided for analysis for the Visit 1 baseline data. It can also apply to subsections of the protocol as long as the specifications are similar to the EPAD Imaging protocol.

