- ^a Visit assessments will be completed within a 21-day window of the planned visit date tethered to the consent form signature date of Visit 1, with the exception of the MRI associated with the visit which should be completed within ± 42 days. The Eligibility will be checked fully at the baseline/visit 1. If a participant develops a condition listed in exclusion criteria e.g. cancer during the follow up period (from visit 2 onwards), the participant may continue in the trial if treating physician and participant agree.
- ^b Before the start of data collection in this study, all research participants must sign a participation agreement/Informed Consent Form (ICF) allowing data collection and source data verification in accordance with local requirements. All informed consents must be taken by the Principal Investigator or medical practitioner who has been delegated to do so.
- ^c All adverse events deemed by clinical judgement to be at least possibly related to EPAD LCS study procedures are to be recorded in the CRF. Adverse event collection should start with the first EPAD LCS procedure and will apply to all adverse events that occur within 30 days after a research participant's last study visit/procedure. When an enrolled participant completes or withdraws from the study, or is lost to follow-up, the investigator will complete the end-of-study form for the individual participant and provide a specific date for the end-of-study observation(s).
- ^d Check for changes since last visit; do not repeat BISQ.
- ^e Sample to be taken at baseline visit
- ^f For SNAC : Participants only report recent events since last visit
- ^g If participant has had a PET amyloid scan in the last 12 months, with results available to EPAD TDC for review and participant is aware of PET results they may choose to defer the baseline lumbar puncture to the 12 month visit. All participants are expected to have at least one lumbar puncture as part of the EPAD LCS cohort.
- ^h Participants may become unable for medical reasons to undergo the CSF sampling procedure. These participants will be allowed to remain in the study without completing CSF sampling future time-points. Participants who score >1 on the CDR will not complete further MRI or CSF sampling, all other assessments will be completed annually.
- ⁱ MRI scan and LP should be collected this year, and then every second year

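### A reused baseline CSF sample or MRI may date from active drug-trial participation, because the 30-day CTIMP exclusion is judged at Visit 1 and not at the sample or scan date

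*Protocol*

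**What the plan says.** Reuse of CSF (Protocol 3.4.3): a sample taken "within 12 months prior to Visit 1, then this sample can be provided for analysis for the Visit 1 baseline data". The condition attached is procedural: it must have been "collected and stored according to the CSF sampling manual procedure (included in the laboratory manual").

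Reuse of MRI (Protocol 3.4.4): a scan to the core EPAD specification done "in the 12 months prior to Visit 1, then this scan can be provided for analysis for the Visit 1 baseline data". The allowance extends to parts of the imaging protocol if the specifications are similar.

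Investigational-product exclusion (Protocol 3.3.2, criterion 10): "Participation in a clinical trial of an investigational product (CTIMP) in the last 30 days". The criterion names no reference date, but footnote a of the Data Collection Schedule states: "The Eligibility will be checked fully at the baseline/visit 1".

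Use of the values: for CSF, section 3.4.3 says "this data will be used for disease modelling and for staging of disease pathology". CSF markers and MRI volumes are also secondary outcomes and are among the selection parameters in section 3.3.3.

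Data recorded: section 3.4.6 lists current medication with a duration band, and a medical history of named conditions plus free text. It has no item for a past investigational product.

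**The concern.** The two rules look back over different periods from the same date. Criterion 10 keeps a procedure done at Visit 1 clear of CTIMP participation in the preceding 30 days. It gives no such protection to a sample or scan obtained months earlier and brought forward as Visit 1 data, and nothing in 3.4.3 or 3.4.4 fills the gap.

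The protocol makes recent trial participants plausible entrants. Table 1 in section 3.2.1 lists "Prevention trial" as one type of parent cohort. Section 3.5.1 mentions leaving an active CTIMP in order to be re-screened. Section 1.1 names "secretase inhibitors, kinase inhibitors and anti-amyloid monoclonal antibodies" among agents then in late-phase trials, and some of these act on the amyloid pathway that CSF Aβ is meant to describe.

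At stake is the meaning of the first biomarker point. After Visit 1 the next scheduled CSF and core MRI are at Visit 4. A baseline obtained on study drug, followed by an off-drug Visit 4 value, could put a drug-withdrawal effect into the change that the disease models read as natural history. The same baseline value also feeds staging and selection.

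**Working it through.** The plan states no figure on this point, so there is none to reproduce. The check is date arithmetic on the two rules.

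**Inputs**
- Maximum age of reused material: 12 months, taken as 365 days (3.4.3, 3.4.4).
- CTIMP look-back: 30 days (3.3.2, criterion 10).
- Anchor of the look-back: Visit 1, inferred from footnote a of the Data Collection Schedule.
- Next scheduled CSF and core MRI: Visit 4, month 24.

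**Condition for the gap.** Let s be the age in days of the sample or scan at Visit 1, and e the number of days before Visit 1 at which CTIMP participation ended.
- The participant passes criterion 10 if e > 30.
- The material dates from active participation if s ≥ e and the trial had begun by then.
- Both can hold only if s > 30. Material aged 30 days or less is not exposed to the gap; material aged 31 to 365 days can be.
- Length of the exposed span: 365 − 30 = 335 days.

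**Example.** CSF taken at day −180; last CTIMP participation at day −60. Since 60 > 30, the participant is eligible. The sample precedes the end of participation by 180 − 60 = 120 days. If the trial was under way by day −180, the on-trial sample is the Visit 1 baseline, and no rule in the protocol stops it.

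**Effect of moving the check.** For illustration, keep the protocol's own 30 days and apply it at the sample date as well.
- A sample at day −180 may then be reused only without CTIMP participation back to day −(180 + 30) = −210. The example fails this check and the Visit 1 lumbar puncture is done.
- At the 12-month limit the check reaches back 365 + 30 = 395 days before Visit 1.
- The span in which reused material can date from active participation falls from 335 days to 0.

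**Interval.** A sample at the 12-month limit makes the nominal 24 months to Visit 4 as long as 24 + 12 = 36 months. The models therefore need the actual sample date whatever the drug exposure.

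**What cannot be computed.** An affected record needs all of the following: CTIMP participation overlapping the sample date and ending more than 30 days before Visit 1; an active arm; a product that shifts the marker; material that meets the EPAD procedure or specification and is available; and a choice to reuse it. The protocol gives no frequency for any of these.

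**The case against.** The passages do not contradict each other. Criterion 10 concerns eligibility, and the reuse provisions spare a repeat procedure. That is right: this is a mismatch of windows, not an outright contradiction.

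The affected group is likely to be small. Reuse is optional, CSF must already meet the EPAD manual, placebo recipients are unaffected, and Table 1 says prevention trial without saying drug trial. This stands and limits the size of the point. A reader might take 335/365, about 92%, as its magnitude. It is only the share of the calendar window that the exclusion leaves uncovered, and says nothing about how many samples are affected.

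A reader might also extend the point to the amyloid PET provision in 3.4.3. The text does not support this. A recent PET lets the participant defer the lumbar puncture to the 12-month visit, so a fresh sample follows and no old CSF value becomes the baseline.

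The laboratory manual, the Balancing Committee criteria and the eCRF are not shown and might restrict reuse or record exposure. Site source records may also hold it. So it would be too strong to say that affected records can never be found; the supported statement is that the listed data items do not identify them.

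Finally, a fresh Visit 1 sample may itself be taken shortly after the 30 days have passed. Any residual effect there belongs to criterion 10, not to this point. The primary endpoint, the RBANS Total Scale Index, has no reuse provision and is not affected by this gap.

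**Conclusion.** The point holds in a limited form. As written, the protocol allows a CSF sample or MRI more than 30 days old at Visit 1 to serve as baseline although it was obtained during active CTIMP participation. For such a participant the baseline level and the first change to Visit 4 may be biased. Whether they are depends on the product and the arm.

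The number affected is unknown and probably small. The conclusion assumes that the 30 days run back from Visit 1 and that no unseen document adds a restriction. It concerns secondary outcomes, staging, selection and the disease models. An analysis plan could not repair it from the listed data items alone, which makes it a data-collection matter and a cheap improvement worth making. A reader might infer that tau-directed agents are a documented risk, but section 1.1 does not name them.

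**What to change.** Reconcile criterion 10 in section 3.3.2 with sections 3.4.3 and 3.4.4, so that the existing CTIMP check also applies at the date of any reused CSF sample or MRI. The sponsor should set the interval. Where the check is not met, the default Visit 1 lumbar puncture or MRI applies.

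Add to the eCRF any prior CTIMP participation, the date of last dose, and the actual date of the sample or scan used as baseline. Affected records can then be flagged or excluded in the disease models, and true intervals used. The record would also show exposure falling wholly between a reused sample and Visit 1, which a check at the sample date alone would miss. For participants already enrolled, these items could be asked at the regular 4-monthly contacts.

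The cost is a short protocol clarification and a few eCRF items. The downside is that a few participants lose the option of reuse and have the procedure that is already standard at Visit 1.

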3.4.4. Neuroimaging Outcomes

Secondary Outcomes

- Hippocampal and whole brain volume

Exploratory outcomes

- Multi-region structural MRI analysis
- Functional regional and network measures

Other Measures

- Vascular burden (WMLs, infarcts, lacunes, microbleeds and superficial siderosis)

Neuroimaging assessments were chosen based on evidence from available studies with an emphasis on secondary prevention of AD (defined from an imaging perspective as amyloid pathology in the brain without necessary signs of accompanying neurodegeneration). Pertinent literature on earlier disease stages covered subjective memory complaints, subjective cognitive impairment and healthy controls. Longitudinal data were mainly considered, but also

cross-sectional data, especially when stratified for amyloid status and APOE4. Another aspect important for EPAD LCS was the usefulness of the imaging data for the subsequent EPAD PoC trial. The choice of imaging assessments additionally factored in participant burden, implementation and costs, while avoiding redundancies between imaging measures and non-imaging procedures.

Magnetic Resonance Imaging (MRI) can provide both structural and functional information about the brain, which confer complementary information regarding disease susceptibility, pathology and impairment. The MRI acquisition is divided into core image acquisition, which all subjects enrolled in the LCS undergo, and advanced image acquisition, which includes functional MRI, which only a sub-set of sites with suitable equipment and experience will acquire.

Investigators that have concerns over a participant's safety undergoing an MRI scan can conduct any safety measures at their discretion (for example, an x-ray to identify metal fragments). The outcome of any safety tests should be recorded in the participant's study notes but will not be reported in the study data. If any safety examinations show a participant cannot undergo an MRI scan, then the participant should be deemed ineligible for the study.

Core MRI Imaging

MRI was chosen because compared to computed tomography it provides lower radiation exposure and the possibility to determine vascular pathology while allowing for quantification of grey matter structures such as the hippocampus and other AD signature regions. MRI is also much better suited to a longitudinal setting, with early-stage subtle changes over time detected in AD-sensitive regions, which can predict future cognitive decline and onset of dementia.

All participants will be required to complete baseline core MRI imaging. Core MRI imaging will be repeated at 2 years (Visit 4) and then every second year for all EPAD research participants. Following visit 1, the MRI scans are scheduled every two years to coincide with the collection of the two yearly CSF sample. The MRI scan precedes the CSF collection as a safety procedure prior to undertaking the lumbar puncture. The core MRI examination for all TDCs (all EPAD LCS participants) are performed to assess study eligibility, for baseline assessment that can be used for subsequent safety monitoring in PoC studies, and for quantitative analysis of brain structure and vascular lesions. Multi-region structural MRI analysis, including whole brain and hippocampal volume analysis, will be performed to better understand how brain volumes change over time in the study population. Alzheimer's Disease Neuroimaging Initiative (ADNI)-like protocols and quality control will be used to ascertain precision in measuring change (direct longitudinal measurement techniques rather than segmentation only). The core MRI examination can be completed in around 30 minutes.

Advanced MRI Imaging

A subset of TDCs that have MRI centres with the necessary technology and experience will additionally acquire more advanced MRI during the same visits as the core MRI listed above. The acquisition of the advanced sequences will depend on the capabilities of the sites and may include on or more of the following types of acquisition:

- 3D-SWI or 3D-T2*
- Diffusion tensor Imaging (DTI)
- Arterial Spin Labelling (ASL)
- Resting state functional MRI (rs-fMRI)

The advanced sequences may extend the scan time, so the total MRI examination could be approximately 45–60 minutes.

If an individual participant has had an MRI to the specification in the Core EPAD Scanning protocol in the 12 months prior to Visit 1, then this scan can be provided for analysis for the Visit 1 baseline data. It can also apply to subsections of the protocol as long as the specifications are similar to the EPAD Imaging protocol.

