3.4.9. Visit Windows

The requirements of the protocol may necessitate the participant attending the clinic on more than one occasions to complete the requirements of each Visit. For Visit 1 all assessments should be completed within 28 days of the first assessment of the visit. For all following visits, all assessments should be completed within ± 21 days of the planned visit date based on the start of the study, i.e. tethered to the first assessment of Visit 1, except the MRI associated with the visit which should be completed within ± 42 days. This provides an 84-day window for each visit following Visit 1. Assessments that take place outside of these windows will be collected and included in the analysis but must be reported as a protocol deviation.

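### Section 3.4.4 lets parts of an earlier MRI that are only similar to the EPAD specification serve as the Visit 1 baseline, against 3.4.3 and its own plan for measuring volume change; prior and delayed baselines also need their true dates

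*Protocol*

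**What the plan says.** **Prior MRI.** Section 3.4.4 provides that, if a participant had an MRI to the Core EPAD specification "in the 12 months prior to Visit 1, then this scan can be provided for analysis for the Visit 1 baseline data". The next sentence extends this to parts of the imaging protocol, "as long as the specifications are similar to the EPAD Imaging protocol". Section 3.4.3 sets a stricter condition for participants with a recent lumbar puncture: they still need a baseline scan "unless they have had an MRI performed to the specifications in the Core EPAD scanning protocol in the 12 months prior to Visit 1". It cites 3.4.4 for this rule.

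**Measuring volume change.** For core MRI, 3.4.4 requires a baseline scan from every participant and a repeat at Visit 4 (2 years). It promises acquisition and quality control on the ADNI model so that change is measured precisely, using "direct longitudinal measurement techniques rather than segmentation only".

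**CSF.** Section 3.4.3 schedules lumbar puncture at Visit 1 and at Visit 4. A sample collected and stored under the EPAD sampling manual is accepted if taken "within 12 months prior to Visit 1, then this sample can be provided for analysis for the Visit 1 baseline data". Participants who know the result of a recent amyloid PET scan have another option: "they may choose to defer the baseline lumbar puncture to the 12 month visit". After a failed first puncture, the sample is to be attempted at Visit 2 or Visit 3. No section moves Visit 4 for anyone with an early or late first sample.

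**Visit 1 timing.** Section 3.4.9 states: "For Visit 1 all assessments should be completed within 28 days of the first assessment of the visit".

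The synopsis lists CSF Aβ, t-tau and p-tau and hippocampal and whole brain volume as secondary outcomes.

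**The concern.** There are two separate issues.

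The first concerns MRI only. Scan-to-scan measurement of brain volume assumes that the two acquisitions match. A baseline that is merely similar, with no criterion and nobody named to judge it, can differ from the follow-up scan in ways that look like tissue change. A correct time variable does not remove this difference, and central reading does not make two acquisitions match.

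The second concerns timing, for both CSF and MRI. A scan or sample up to a year old carries the Visit 1 label next to an RBANS score obtained within the 28-day window. A first CSF sample may also come up to a year after that score. If the data carry only the visit label, the interval to Visit 4 is misstated, and baseline biomarker and baseline cognition are treated as simultaneous when they are not. These measures feed the joint modelling of cognition and biomarkers in section 4.3. For participants who leave for the PoC trial after baseline, which the synopsis allows, the baseline biomarker may be the only one they have.

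**Working it through.** **1. The two MRI rules side by side**

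- Section 3.4.3: the baseline scan is waived only for an MRI to the Core specification.
- Section 3.4.4, first sentence of the rule: the same standard.
- Section 3.4.4, second sentence: parts of a scan need only be similar. The volumetric sequence is not excluded.
- Section 3.4.4, core imaging: precision of volume change depends on standardised acquisition and direct longitudinal measurement.

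The second sentence can therefore admit a volumetric baseline that 3.4.3 would not, for an outcome that the core imaging text says needs matched measurement.

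**2. The protocol's own interval**

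Interval = month of Visit 4 − month of first acquisition. On schedule this is 24 − 0 = 24 months, which agrees with the stated 2 years.

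**3. The intervals the rules permit**

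| Measure | First acquisition | Month | Interval to Visit 4 | Ratio to 24 |
|---|---|---|---|---|
| CSF | stored sample, oldest allowed | −12 | 36 | 1.50 |
| CSF | on schedule | 0 | 24 | 1.00 |
| CSF | retry at Visit 2 | +6 | 18 | 0.75 |
| CSF | PET deferral or retry at Visit 3 | +12 | 12 | 0.50 |
| MRI | prior scan, oldest allowed | −12 | 36 | 1.50 |
| MRI | on schedule | 0 | 24 | 1.00 |

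The windows in 3.4.9, at 30.44 days per month, widen these ranges slightly:

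- CSF: 12 − (21 + 21)/30.44 = 10.6 to 36 + 21/30.44 = 36.7 months.
- MRI: 24 − (28 + 42)/30.44 = 21.7 to 36 + 42/30.44 = 37.4 months.

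In one participant the MRI baseline (−12) and the first CSF sample (+12) could be 24 months apart.

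**4. What visit indexing would do (conditional illustration)**

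Suppose change is linear and every Visit 4 change is read as a 24-month change. One participant's apparent annual rate is then interval/24 times the true rate: 36/24 = 1.5 for the oldest baseline, and 12/24 = 0.5 for a month-12 sample, if that sample were treated as Visit 1.

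For the group mean, let p be the share with a −12-month baseline and q the share with a +12-month CSF sample. The relative error is (12p − 12q)/24 = (p − q)/2. The protocol gives neither share, so these are assumed:

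- p = 5%, 10%, 20%, 30% with q = 0: mean change overstated by 2.5%, 5%, 10%, 15%.
- q = 5%, 10%, 20% with p = 0 (CSF only): mean change understated by 2.5%, 5%, 10%.

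With actual dates as the time variable, this interval error is zero.

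**5. What an acquisition offset would do (conditional illustration)**

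The protocol gives no figures. Assume hippocampal loss of 0.5% to 1.5% per year and an offset between non-matching sequences of 2% to 5% of volume. Offset divided by yearly loss gives:

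- 2/1.5 = 1.3 years
- 5/1.5 = 3.3 years
- 2/0.5 = 4 years
- 5/0.5 = 10 years

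The last figure pairs the largest assumed offset with the slowest assumed loss. The planned interval is 2 years.

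**The case against.** The strongest reply concerns rates of change. Section 4.3 plans mixed-effects models, then latent trajectory and Gaussian-process models, and all of these can use each participant's own times. Section 3.4.9 already takes off-schedule assessments into the analysis. The time variable is normally fixed in the statistical analysis plan, which is not at hand. This stands: a reader might infer that the CSF and MRI rates will be wrong by factors of 0.5 to 1.5, but no section fixes a 24-month divisor.

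The labelling point is also narrower than it may look. Only stored samples and prior scans are called Visit 1 data. Deferred punctures are placed at the 12-month visit and retries at Visit 2 or 3, so nothing shows that a month-12 sample would be entered as Visit 1. This stands too.

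A third reply is that the relaxed wording covers only parts of a scan and follows directly after the advanced sequences, which vary by site, so volumetry may never have been meant. That is possible, but the text does not say so. The reply shows how easily the wording can be repaired, not that it is sound.

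Finally, the 12-month allowances can be read as explicit exceptions to the 28-day rule that spare participants repeat procedures. That is a fair reading. It removes a formal contradiction with 3.4.9 but not the need to know when each baseline was acquired.

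**Conclusion.** The point holds in two parts, and the change is inexpensive.

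**MRI acquisition.** The wording of 3.4.4 is looser than that of 3.4.3 and does not fit the measurement approach that 3.4.4 itself sets out. As written, it can put non-matched scans into hippocampal and whole brain volume change. The size is unknown: it depends on how often the allowance is used for volumetry and on the offset, and the figures for the offset above are assumptions.

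**Timing.** First-to-second intervals are nominally 12 to 36 months for CSF and 24 to 36 months for MRI, against a stated 24. Rates are distorted only under visit-indexed analysis. Actual dates remove the interval error, but a baseline biomarker may still lie up to 12 months from the Visit 1 RBANS. The share of participants affected is unknown.

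Four stronger readings are not supported:

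- That acquisition differences affect CSF. Prior samples must follow the EPAD manual, and section 3.4 sends CSF to central laboratories.
- That MRI intervals can be as short as 12 months. Only CSF can be deferred or retried.
- That the participants concerned have already been worked up clinically. Most come from parent cohorts and AMYPAD co-enrolment is allowed, so prior scans may be research data. The text shows only that PET deferral requires a known PET result.
- That prior scans must come from the scanner used at follow-up. The protocol asks this of no scan.

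**What to change.** 1. In section 3.4.4, state that an earlier scan supplies Visit 1 hippocampal or whole brain volume only if its volumetric sequence met the Core EPAD specification. Parts that are only similar may serve other readings, such as vascular burden. This brings 3.4.4 into line with 3.4.3.

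2. In sections 3.4.3 and 3.4.4, record every prior, deferred or retried sample and scan under its actual acquisition date, with a flag for its source. State that these dates are the time variable for biomarker change and for pairing biomarkers with RBANS.

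3. Add a sensitivity analysis that leaves out baselines acquired outside the Visit 1 window.

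The cost is a few sentences of protocol text, a date and source field in the database, and one further analysis. The downside is that a few participants with a non-Core earlier scan would lack a volumetric baseline or need the Core scan.
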